### **3.3 Study Significance**

Prior studies evaluating variability in drug response are confounded by the highly variable ATX exposures between children, even when given the same weight-based dose, and hence are difficult to interpret (e.g., is a patient truly non-responsive to the medication, or is “non-response” simply due to having inadequate concentrations of the medication in the body). In this investigation we propose to individualize ATX dosing in a cohort of children with ADHD to a standardized exposure goal (based on the maximum concentration achieved, or  $C_{max}$ ), initially using a iGO-PK model derived from our original genotype-stratified PK study, and assign responder or non-responder status according to response criteria established *a priori* by the clinical members of the study team.

Subsequent analyses will investigate predictors of response (metabolomics analysis of pretreatment plasma samples; assessment of biomarkers of ATX inhibition of SLC6A2, such as dihydroxyphenylglycol (DHPG) concentrations and pupil diameter and eye-tracking studies; SLC6A2 genotype; pharmacokinetic-pharmacodynamic (PK/PD) analysis of ATX and DHPG data, etc), as well as differences in exposure→response relationships for different DHPG strata or SLC6A2 genotypes. In addition, the dosing algorithms (iGO-

[figure not shown]
PK) will be updated and revised as the body of pharmacokinetic data increases through the duration of the study.

## 4.0 Study Endpoints and Rationale

### 4.1 Primary Study Endpoints

The primary aims of this study focus on characterizing the relationship between changes in pharmacodynamic markers and clinical outcome measures, when inter-subject variability in ATX pharmacokinetics has been minimized (Fig. 3). ATX pharmacodynamics will be measured using plasma DHPG and metabolomic data, pupillometry during attention tasks, and changes in blood pressure and heart rate. Clinical outcomes will be assessed by standardized ADHD measures used in a clinical setting, of which include: NICHQ Vanderbilt Assessment Scale (ADHD symptom rating scale); Strengths and Difficulties Questionnaire; Child Behavior Checklist; the School Intervention Questionnaire; Medication Side Effects; and Clinical Global Impression. Some of these questionnaires will also capture comorbidity information, such as Oppositional Defiant Disorder (ODD). We will also use the Kiddie Schedule for Affective Disorders and Schizophrenia for School-Age Children – Present and Lifetime Version (K-SADS-PL) or K-SADS-COMP (the computerized version of the K-SADS-PL) to diagnose ADHD and commonly associated comorbidities. The K-SADS-PL is a semi-structured interview that is extensively used in clinical psychology research to diagnose an extensive array of psychopathology based on the DSM-5. Given the length of this interview, common research practices are to select only the modules that are expected to be pertinent to the study participant (Black et al., 2012; Kariuki et al., 2018; Caudle et al., 2020). The K-SADS-PL modules selected for this research study are as follows: agoraphobia, separation anxiety disorder, social anxiety disorder/selective mutism, specific phobias, generalized anxiety, obsessive compulsive disorder, and post-traumatic stress disorder. The other research comorbidities or impairments that we will assess for and associated psychometric tests we will use are as follows: impairment in executive function using the Behavior Rating Inventory of Executive Function (BRIEF); anxiety using the Screen for Child Anxiety and Related Disorders (SCARED); intelligence quotient using the Kaufman Brief IQ Test (KBIT); and sluggish cognitive tempo using the Barkley Sluggish Cognitive Tempo Scale (SCT). Pharmacodynamic data will be obtained: baseline (Research Visit 1); when ATX is first initiated in a participant with the first dose (Research Visit 2); when the participant has taken the medication chronically and thus, expected to be at steady-state (Research Visit 3); and at the end of study when the dose has been optimized for the participant (Research Visit 4). Concurrent pharmacokinetic analysis will take place to ensure that ATX plasma and urine exposure variability has been minimized using methods described in a previous ATX pharmacokinetic study conducted at Children's Mercy Hospital (Brown et al., 2016). Additionally, we will measure ATX and metabolites in sweat as surrogate for fraction of drug unbound (Marchei et al., 2012; Marchei et al., 2013). The clinical ADHD questionnaires will be administered at the Intake Visit and at follow-up visits following initiation of atomoxetine treatment (6-weeks, 12-weeks, and

18 weeks). These questionnaires ask the participant's parents and teachers to rate behaviors characteristic of ADHD. Changes in other comorbidities associated with ADHD, such as anxiety or sluggish cognitive tempo, will be evaluated at Research Visit 1 and at Research Visit 4. We will also simultaneously monitor side effects of ATX, another measure of clinical outcomes, and categorize study participants on their ability to tolerate ATX. Adverse events will be assessed at all encounters between the study personnel and study participant. At Research Visit 4, we will also administer the Dietary Survey Questionnaire, given that long-term dietary habits may affect both ATX pharmacokinetics and pharmacodynamics.

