### **8.2 Target Participants**

The research proposal targets 160 participants who are expected to be enrolled and screened. The target number of subjects needed to complete research procedures is 120. Participants who complete at least Research Visits 1-3, the Intake Visit, and the 6-Week Visit with the Study Physician will be considered to have "partially completed" the study. Completion of these visits will include obtaining baseline measurements, confirmation of eligibility, single and steady-state PK and PD measurements, and at least one post-treatment clinical response assessment. Since data from these participants will meet the study aims, those who partially complete the study will be counted toward the 120.

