18-Week Visit with Study Physician – The participant and family meet with a study physician approximately 6 weeks after the 12-Week Visit with Study Physician. A ± 2-week window is allowed for ease of scheduling. Prior to this visit, questionnaires will be sent out via CHADIS to parents and teachers to assess participant's behavior. During this visit, safety, efficacy, and side effects will be assessed and dose adjustments will be made accordingly. In addition, baseline questionnaires will be re-administered to gauge symptom and impairment changes post-treatment initiation. Dose adjustments may be outside research and visits with study physicians as needed.

Research Visit 4 – This visit is also referred to as pharmacokinetic study 3 (PK3) or end of study PK. This vist occurs after the 18-Week Visit with Study Physician. This visit takes place in the PCRU and consists of the same procedures as Research Visit 3. Determination of Study Design will be confirmed prior to visit, as some participants may require switching to a different study design if frequency of dosing has changed. During this visit, baseline psychometric measures will be re-administered to measure change post-treatment initiation. An end of study EKG will be obtained, and a Dietary Survey Questionnaire will be administered.

- Description of Research Procedures

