    - x.* Administer end of study psychometric questionnaires:
      - i.* Screen for Child Anxiety Related Disorders (SCARED parent and participants  $\geq$  8 years old informant).

- ii.* Barkley's Sluggish Cognitive Tempo (SCT) (parent informant).
    - iii.* Behavior Rating Inventory of Executive Function (BRIEF) (parent informant. Teacher informant is optional).
  - y.* Administer Dietary Survey Questionnaire (participant informant).
- z.* Please note that the SCARED and the BRIEF are validated tools that are used to aid the Study Physician in determining treatment response. Use of different versions of these questionnaires are permissible to aid the Study Physician, in addition to clinical impression, with medication management and determination of response.
  - aa.* Assess for adverse events. Document in Adverse Events log.
  - bb.* Determine and document participant's adherence to ATX medication regimen.
    - i.* High adherence is defined as the participant taking  $\geq$  80% of their scheduled doses
    - ii.* Medium adherence is defined as the participant taking between 40 – 79% of their scheduled doses.
    - iii.* Low adherence is defined as a participant taking  $<$  40% of their scheduled doses.

11.1.1.1 Add compensation to participant's Greenphire account.

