## SHORT TITLE: ATX-PBPK-PD-Clinical Outcomes (U54)

Pharmacokinetic sample (urine)				X	X				X	
Microbiome sample (saliva)		X		X	X				X	
Schedule of Events	Prescreen	Research Visit 1* θ	Intake with Study Physician ψ	Research Visit 2*	Research Visit 3*	6-Week Visit with Study Physician ψ	12-Week Visit with Study Physician ψ	18-Week Visit with Study Physician ψ	Research Visit 4*	2-week Post-Study Check
Sweat patches (sweat)				X	X				X	
Pupillometry during Posner's Cuing Task		X		X	X				X	
Dietary Survey Questionnaire									X	
Kiddie Schedule for Affective Disorders and Schizophrenia (KSADS)		X								
Kaufman Brief IQ Test (KBIT)		X								
Behavior Rating Inventory of Executive Function (BRIEF)		X							X	
Barkley Sluggish Cognitive Tempo Scale (SCT)		X							X	
Screen for Child Anxiety and Related Disorders (SCARED) – parent		X							X	

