## 17.0 Risks to Subjects

- Confidentiality Risk: There is a risk of loss of confidentiality. Confidentiality will be protected to the greatest extent possible. There is also a risk of loss of confidentiality when using the internet. This is especially pertinent when filling out questionnaires using a web interface. The study team will make every effort to protect the participant’s confidentiality such that this risk is minimal.
- Blood Draw: Risks of drawing blood include discomfort and/or bruising. A needlestick can be greater than minimal risk. However, numbing spray and topical lidocaine can be provided to minimize pain associated with needle sticks. In addition, the study team will inquire about needlestick fears and comfort techniques prior to the first needlestick.
- Allergic reaction: It is possible to have an allergic reaction to atomoxetine. Currently, there is no way to predict whether an individual will have an allergic reaction to atomoxetine *a priori*. However, the percentage of individuals experiencing allergic reaction is low. The first dose of atomoxetine will be administered

to the participant in the PCRU. Medications and procedures are in place should a participant have an allergic anaphylactic reaction to atomoxetine.

- Genetic Risks: The unauthorized disclosure of genetic information may have an impact on a participant's employability, insurability, immigration status, paternity suits, or social reputation. These risks include the chance of discrimination. The study team will make every effort to protect the participant's genetic such that this risk is minimal. Additionally, the genes investigated in the study have thus far only been associated with drug pharmacokinetics and pharmacodynamics. The risk of discrimination with this type of genetic information is lower compared to genes linked to predisposition of disease.
- Side Effects Risks: Participants may experience side effects of atomoxetine related to the way the medication is dosed. Typical side effects include increased heart rate, headache, stomach upset, nausea, sleepiness, and emotional lability. In addition, there are reports of suicidal ideation with atomoxetine use. The level of risk is variable given that the severity of side effects can be different among participants.

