#### *Global Neurotransmitter Analysis*

$k_{in, DHPG}$	Rate at which DHPG is created endogenously
$k_{out, DHPG}$	Rate at which DHPG is catabolized endogenously
$I_{max, DHPG}$	Maximal fractional inhibition produced by ATX
$IC_{50, DHPG}$	Concentration of ATX that results in 50% of maximal inhibition
$E_{max, DHPG}$	Maximum response through interaction of drug and drug target
$EC_{50, DHPG}$	Concentration of ATX that results in 50% of maximal response

Rates of formation and elimination ( $k_{in}$  and  $k_{out}$ ), maximal inhibition ( $I_{max}$ ), concentration at which 50% maximal inhibition is achieved ( $IC_{50}$ ), maximal response ( $E_{max}$ ), and concentration at which 50% maximal response is achieved ( $EC_{50}$ ) will be determined for all neurotransmitters assessed in the global neurotransmitter panel (see Appendix I for metabolite list). The Dietary Survey Questionnaire and microbiome information from saliva samples will be analyzed as possible covariates of the neurotransmitter profiles.

**Genetic Analysis:** Genome-wide analysis and single nucleotide polymorphism (SNP) analysis will be conducted on participant samples. Genetic testing (microarray SNP analysis, PCR sequencing, etc.) will be conducted to characterize variants in genes involved in disposition and response of ATX. Some examples of genes that may affect drug disposition and response include, but are not limited to, *CYP2D6*, *CYP2C19*, *ABCB1*, and *SLC6A2*. Genes associated with ADHD phenotype may also be analyzed, especially if ATX response (or lack thereof), is associated with a particular sub-population of individuals with ADHD. Additional testing may be conducted should more information become available regarding genes that may affect the prescribed drug's pharmacokinetic profile, pharmacodynamic characteristics, or clinical outcomes (i.e. safety, efficacy, or toxicity). Information on variants will be analyzed to determine impact on ATX safety, efficacy, or toxicity.

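### The only long-term diet measure is collected at Research Visit 4, so this candidate covariate has no pre-treatment value and is absent for children who leave earlier

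*Combined protocol and SAP*

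**What the plan says.** Section 4.1 gives both the timing and the reason for the Dietary Survey Questionnaire: "At Research Visit 4, we will also administer the Dietary Survey Questionnaire, given that long-term dietary habits may affect both ATX pharmacokinetics and pharmacodynamics." The visit overview in 11.1 repeats the timing: "An end of study EKG will be obtained, and a Dietary Survey Questionnaire will be administered." It also says that RV4 "occurs after the 18-Week Visit with Study Physician". Section 11.4 describes the form as a record of long-term dietary patterns and states no recall period.

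The form's analytic role is one sentence in 20.1, under Global Neurotransmitter Analysis: "The Dietary Survey Questionnaire and microbiome information from saliva samples will be analyzed as possible covariates of the neurotransmitter profiles."

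On who is counted, 8.2 says that "those who partially complete the study will be counted toward the 120". Partial completion means RV1 to RV3, the Intake Visit and the 6-Week Visit. Section 20.1 admits the same children to the outcome analysis linked to pharmacodynamics, provided their pharmacokinetic and pharmacodynamic data are sufficient.

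**The concern.** The plan regards diet as something that may act on drug levels and drug effect. A covariate in that role is best measured before the drug is started, and here it is measured only near the end of treatment. Two consequences follow.

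- **Timing.** There is no diet value from the time of the pre-dose neurotransmitter sample. Section 17.0 says of atomoxetine: "Typical side effects include increased heart rate, headache, stomach upset, nausea, sleepiness, and emotional lability." Stomach upset and nausea could change what a child eats, so diet reported at RV4 may partly be a result of treatment. Adjusting on-treatment profiles for such a variable could absorb some of the drug effect that the model is meant to estimate.
- **Missingness.** A child who leaves before RV4 has no form. If leaving is related to response or tolerability, the children with a diet value are a selected group, and a complete-case model adjusted for diet would describe that group only.

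**Working it through.** The plan gives no figure to reproduce on this point. The check is a comparison of sections, plus simple arithmetic.

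**1. When the form is given.** Section 4.1, the RV4 overview in 11.1, the RV4 procedures in 11.2 and the Schedule of Events (one mark, in the RV4 column) all agree. No administration is described at RV1, RV2 or RV3, in the withdrawal procedures (16.2), or at the two-week post-study call.

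**2. Time on drug at RV4.** The Schedule of Events places the physician visits 6 weeks apart, each counted from the one before, with a window of ± 2 weeks.
- Nominal: 6 + 6 + 6 = 18 weeks.
- All windows early: 3 × (6 − 2) = 12 weeks.
- All windows late: 3 × (6 + 2) = 24 weeks.

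RV4 follows the last of these visits, so the form is completed after at least about 12 weeks on drug.

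**3. Diet beside comparable measures (11.2 and Schedule of Events).**

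| Measure | Before first dose | On treatment |
|---|---|---|
| Neurotransmitter blood sample | RV1 Part 2 | RV2, RV3, RV4 |
| Saliva for microbiome (the other named covariate) | RV1 Part 2 | RV2, RV3, RV4 |
| BRIEF, SCT, SCARED | RV1 Part 2 | RV4 |
| Visit-day meal times and content (not named as a covariate) | none described | RV2, RV3, RV4 |
| Dietary Survey Questionnaire | none | RV4 only |

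Of the two covariates named for the neurotransmitter profiles, only diet lacks a baseline.

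**4. Who lacks the form.** A child who meets the partial-completion rule and then leaves before RV4 has no form. Three provisions tie some exits to outcome:
- 4.2 defines intolerance as side effects that lead to stopping the drug and leaving the study (20.1 has a broader criterion).
- 16.1 lists a symptom reduction below 10% at the 12- and 18-week visits as a ground for withdrawal, and both visits precede RV4.
- 20.1 classes children who stop early for perceived lack of efficacy as non-responders.

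**5. Size.** The documents give no rate of leaving between the 6-Week Visit and RV4. The 20% attrition in 20.2 is not defined for that interval. By assumption only:

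| Assumed share of 120 leaving | Without form | With form |
|---|---|---|
| 0% | 0 | 120 |
| 10% | 12 | 108 |
| 20% | 24 | 96 |
| 30% | 36 | 84 |

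To show what selection could do at the extreme, take the 30% response rate of 20.2: 0.30 × 120 = 36 responders. If 24 children left and all were non-responders, responders would be 36/96 = 37.5% of those with a form, against 30% overall. If leavers had the same mix as the rest, the share would stay at 30%.

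**The case against.** The case for leaving the plan alone has real substance.

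- **The use is exploratory.** Section 20.1 names diet only as a candidate covariate. A reader might infer that the comparison of baseline profiles between responders and non-responders will be adjusted for diet. The plan does not say so: that comparison is a PLS-DA with variable-influence scores and no diet term. The covariates listed for telling the two groups apart come from the initial clinic visit and do not include diet.
- **The form targets habitual diet.** Answers at RV4 may partly describe eating before treatment. It would go too far to say that the RV4 value is a consequence of the drug. The recall period is not stated, and 17.0 lists stomach upset and nausea without saying that diet changes.
- **Some food data exist earlier.** Meals are documented on the day of RV2, RV3 and RV4, so it is wrong to infer that partial completers have no dietary record at all. These are single-day records with no assigned analytic role.
- **Missingness is not confined to one group.** Non-response is a reduction below 40% together with a Clinical Global Improvement score of 3 or more. The withdrawal ground is a reduction below 10%. Children between those limits can reach RV4, and 16.1 also lists exits such as loss to follow-up and non-compliance.
- **Missing data are mentioned.** Section 20.2 says that weighting or imputation will be considered, and no complete-case analysis is prescribed.

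These arguments limit the point to a possible bias in an exploratory model. They do not supply a pre-treatment diet value, and the general remark in 20.2 does not say how a missing diet form will be handled.

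**Conclusion.** The point holds as a cheap improvement, not as a flaw in a primary analysis. Long-term diet is measured once, nominally about 18 weeks and at least about 12 weeks into treatment. It has no value to pair with the RV1 neurotransmitter profile, and it is absent for every child who leaves before RV4. Some of those exits are linked to outcome. The size of the loss and of any bias cannot be computed from the documents; the 12 to 36 children above rest on an assumed 10% to 30% exit rate. The documents do not support a stronger conclusion that the responder comparison is biased by diet adjustment, or that the form is missing for non-responders as a class. No sample-size figure depends on it.

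**What to change.** - **Collection.** In 4.1, 11.2 (RV1 Part 2), 11.4 and the Schedule of Events, add the existing questionnaire at RV1 Part 2, before the first dose. State its recall period in 11.4.
- **Analysis.** In 20.1, use the RV1 form wherever diet is a covariate of baseline or on-treatment profiles. Analyse the RV4 form only as change in diet on atomoxetine.
- **Children with only an RV4 form, or none.** Report the neurotransmitter models with and without diet. Fit the unadjusted model to all children, including those without a form, and repeat it in the children who have one. The effect of adjusting can then be told apart from the effect of losing children. State in 20.1 how a missing form is handled.

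The cost is an amendment, a line in the RV1 checklist and a few more minutes at RV1. Only children not yet past RV1 benefit from the new collection, and there may be few: revision 17.0 is dated October 2021, and 10.1 expects study procedures to finish around June 2022. The analysis changes apply to everyone and need no new data.

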**Fig 3. - Analysis of Study Endpoints**

ATX is thought to exert its therapeutic effect in ADHD through inhibition of the presynaptic norepinephrine (NE) transporter (NET) encoded by the *SLC6A2* gene. NE is involved in several neuropsychological functions, including visual attention, general alertness, sustained attention, learning and memory and executive functions; dysregulation of NE homeostasis has been implicated in the development of ADHD. Consequently, there has been considerable interest in *SLC6A2* as a candidate gene for ADHD, but the results of studies investigating associations between *SLC6A2* allelic variants and ADHD and related phenotypes have been inconsistent and discordant. Of

interest is rs28386840, also known as *SLC6A2 -3081 A>T*, in the regulatory region of the *SLC6A2* gene. The minor -3081 T allele has been associated with a reduction in promoter activity, which would result in lower expression of the NET transporter.

*In vitro*, as well as *in vivo* animal and human studies have provided evidence that plasma concentrations of 3,4-dihydroxyphenylglycol (DHPG) are derived predominantly from NE inside nerve cells. As a consequence, inhibition of NE reuptake by ATX is accompanied by decreases in NE inside presynaptic nerve cells, and subsequently, decreases in plasma DHPG concentrations. Published studies in adults indicate that DHPG concentrations in plasma progressively decrease for the first four hours following ATX administration and gradually recover in 24 hours; comparable data in children with ADHD receiving ATX have not been reported. In contrast, single doses of a structurally related norepinephrine reuptake inhibitor, edivoxetine to adolescents produced an average reduction in baseline DHPG of 28% across all tested doses. With chronic dosing, the reduction in DHPG concentration persisted for at least 12 hours. Of particular interest is the observation that no reduction from baseline was observed in two subjects, both of whom had relatively low baseline concentrations of 431 pg/ml and 657 pg/ml and for whom the lack of response could not be attributed to low drug exposure; no information regarding clinical response was provided. These considerations provide the basis for assessing DHPG as a potential biomarker of clinical response to ATX, and specifically for investigating the relationship between the magnitude of reduction in plasma DHPG concentration as a function of ATX concentration, and how it translates into clinical response in children with ADHD. As ATX selectively binds to NET in the prefrontal cortex and modulates the reuptake of not only norepinephrine, but also dopamine, we propose to conduct a comprehensive analysis of neurotransmitters, including norepinephrine, dopamine, DHPG and several of the breakdown products (see Secondary Aims). (Kielbasa et al., 2009; Kielbasa and Lobo, 2015; Kielbasa et al., 2015). A similar approach has been applied to serotonin selective reuptake inhibitors for adults with major depressive disorder. Responders and non-responders citalopram/escitalopram displayed significantly different baseline metabolomics signatures (Kaddurah-Daouk et al., 2011).

